1. To compare duration of need for supplemental oxygen and/or mechanical ventilation between recipients of the anti-SARS-CoV-2 plasma and control plasma.
2. To compare duration of hospitalization between recipients of the anti-SARS-CoV-2 plasma and control plasma.

3. To compare in-hospital and 28-day mortality between recipients of the anti-SARS-CoV-2 plasma and control plasma.

Ancillary Endpoints:

1. To compare the proportion and duration of SARS-CoV-2 PCR positivity (RT PCR) between recipients of the anti-SARS-CoV-2 plasma and control plasma at days 0, 7, and 14.
2. To compare the levels of SARS-CoV-2 RNA between recipients of the anti-SARS-CoV-2 plasma and control plasma at days 0, 7, and 14.
3. To compare genetic differences between recipients of the anti-SARS-CoV-2 plasma and control plasma to explore possible associations with poor outcome.
4. To compare transcriptomic differences between recipients of the anti-SARS-CoV-2 plasma and control plasma at Day 0, 7, and 14 to explore possible associations with poor outcome.

Definitions

Enrolled: From time consented to participate until designated as a screen failure or have either been discontinued from the study or completed it. II. Randomized: when a study arm is assigned. III. Screen Failures: signed informed consent, but then determined to be ineligible or withdraws before being randomized. IV. Discontinued: randomized, but then withdrawn by investigator or withdraws consent. V. Completed: Subjects are considered completed when they are followed through to day 28, if they die before day 28, or are discharged prior to day 14.

Study population

Inclusion Criteria for Enrollment 1. Willing and able to provide written informed consent prior to performing study procedures or having a legally authorized representative available to do so. 2. Age ≥ 18 years. 3. Evidence of SARS-CoV-2 infection by PCR test of nasopharyngeal swab or oropharyngeal swab/tracheal aspirate sample within 14 days of randomization 4. $\text{SpO}_2 \leq 94\%$ on room air or requiring supplemental oxygen, non-invasive or invasive mechanical ventilation at screening 5. Evidence of infiltrates on chest radiography 6. Females of childbearing age and males must be willing to practice an effective contraceptive method or remain abstinent during the study period.

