Exclusion Criteria for Enrollment 1. Participation in another clinical trial of anti-viral agent(s)* for COVID-19 2. Receipt of any anti-viral agent(s)* with possible activity against SARS-CoV-2 < 24 hours prior to plasma infusion. 3. Mechanically ventilated (including VV-ECMO) ≥ 5 days 4. Severe multi-organ failure 5. History of allergic reactions to transfusion blood products per NHSN/CDC criteria 6. Known IgA deficiency 7. Females who are pregnant or breastfeeding. *Use of remdesivir as treatment for COVID-19 is permitted.

Subject Withdrawal

Subjects can terminate study participation and/or withdraw consent at any time without prejudice. II. Randomized subjects who withdraw from the study will not be replaced. III. The investigator may withdraw subjects if they are lost to follow up, non-compliant with study procedures or if the investigator determines that continued participation in the study would be harmful to the subject or the integrity of the study data. IV. Discontinuation of the study: The study sponsor, FDA and IRB all have the right to terminate this study at any time.

Intervention

Subjects will be randomized in a 2:1 ratio, stratified by country, to receive treatment vs. frozen fresh plasma. II. Study drug: The investigational product is anti-SARS-CoV-2 plasma. Patients identified as having recovered from COVID-19 will serve as potential donors. Testing will confirm presence of anti-SARS-CoV-2 antibody prior to donation. Potential donors and samples will be screened for transfusion-transmitted infections (e.g. HIV, HBV, HCV, WNV, HTLV-I/II, T. cruzi, ZIKV) and plasma will be collected using apheresis technology. This is similar to standard blood bank protocols. III. Active arm will receive 1 unit of anti-SARS-CoV-2 plasma. IV. Control arm will receive 1 unit of control plasma. V. The study drug will be in a standard plasma unit bag, with a studyspecific ISBT label and will include the following statement: "Caution: New Drug--Limited by Federal (or United States) law to investigational use." VI. The blood bank will not be blinded to treatment allocation, nor will the clinical study team. VII. The patient and the clinician who will assess the end of treatment outcome will be blinded to treatment allocation.

Randomization

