Subjects enrolled in the study will be randomized to receive study drug vs. control using a web-based randomization platform that will pre-generate all treatment assignments in a 2:1 ratio using random permuted blocks of random block sizes, stratified by country (US and Brazil) The assignment list is maintained by designated staff at the DCC, independent from the study, and then sent to the Principal Investigator/research team for each participant that is deemed eligible.

Study product considerations

The preparation of the anti-SARS plasma and the control plasma will take place at the New York City Blood Center and the CUIMC-NYPH Blood Bank will dispense the plasma products. The plasma collection procedures are not part of this research protocol and are described in separate protocols, which has separate IRB approval (AAAS9845). The description below provides a summary of study product considerations as context.

Collection:

All activities pertaining to the collection and processing of plasma will take place at [New York Blood Center/NYBC]. NYBC is one of the largest independent, community-based, nonprofit blood centers in the United States. NYBC has a longstanding research program and is well versed in the regulatory and ethical aspects of research, including clinical trials. The organization is FDA-licensed to produce convalescent plasma and AABB (American Association of Blood Banks) accredited, attesting to robust quality oversight of all operations. The donation and collection of donor convalescent plasma will occur under CUIMC IRB protocol AAAS9845.

Collection and processing:

- Standard apheresis plasma collection will be performed per routine standard operating procedure at the collection facility (NYBC). • As per routine practice, samples will be collected at time of donation for testing for transfusion-transmissible infections (all donors), ABO and red cell antibodies (all donors) and HLA antibodies (female donors with prior pregnancies). • Target collection volume: ~450-600mL; this will allow for later splitting (separation) into 200-250mL daughter units. • The plasma will be processed

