4. Missing data and non-compliance

We will compare the missing data patterns between the study arms; and perform sensitivity analyses using different imputation approaches. However, due to the short study period, we anticipate minimal missing data. All efficacy analyses will be done intent-to-treat, although as-treat analyses will also be conducted as sensitivity.

STUDY PROCEDURES

Screening

- A. Screening (must be completed before randomization)
- B. Informed consent (obtained before performing study related activities)
- C. Baseline Evaluation (at screening) 1. Demographics (age, sex, ethnicity, race) 2. Medical history (acute and chronic medical conditions, medications, allergies) (any medical condition arising after consent should be recorded as AE) 3. COVID-19 symptom screen (fever, cough, shortness of breath) 4. Confirmation of SARS-CoV-2 testing (RT-PCR) for eligibility (within 14 days of randomization) 5. Vital signs 6. Physical examination 7. Blood typing 8. Urine or serum pregnancy test for females of childbearing potential. Results from laboratory tests obtained up to 7 days before enrollment may be used for the pregnancy test. 9. Determination of eligibility as per inclusion/exclusion criteria

Baseline (Randomization)

- 1. Randomization of eligible subject 2. Vital signs 3. COVID-19 symptom screen (fevers, cough, shortness of breath) 4. New medical conditions, concomitant medication 5. Assessment of clinical status (using 7-point ordinal outcome scale) 6. CBC, comprehensive metabolic panel (abstracted from routine clinical lab results in electronic medical record) 7. Stored samples for future studies (only if feasible) 8. SARS-CoV-2 testing (RT-PCR) from nasopharyngeal swab (only if feasible)

Day 0 Infusion (Within 48 hours from randomization) 1. Study Plasma Administration: A single unit of plasma will be transfused. Time at start and end of infusion will be recorded and vital signs will be measured immediately prior to infusion, 10-20 minutes after start of infusion, and at completion of

infusion. 2. Vital signs 3. Physical examination (acceptable to use clinician notes from electronic medical record) 4. COVID-19 symptom screen (fevers, cough, shortness of breath) 5. New medical conditions, concomitant medication, AE evaluation

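### A study team that knows the arm may withdraw randomized patients, and the protocol does not provide for obtaining their Day 28 status, so outcomes can go missing by arm

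*Combined protocol and SAP*

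**What the plan says.** Subject Withdrawal, item III, states: "The investigator may withdraw subjects if they are lost to follow up, non-compliant with study procedures". It adds a further ground, at the investigator's judgment, where "continued participation in the study would be harmful to the subject or the integrity of the study data". Item II of the same section says that randomized subjects who withdraw are not replaced.

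Definitions, item IV, classes such a patient as discontinued: "randomized, but then withdrawn by investigator or withdraws consent". Enrolled status ends at discontinuation or completion. Completed is a separate status, which covers follow-up to Day 28, death before Day 28, or discharge before Day 14.

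On knowledge of the arm, Intervention, item VI, says "The blood bank will not be blinded to treatment allocation, nor will the clinical study team". Under Randomization, each assignment is "sent to the Principal Investigator/research team for each participant that is deemed eligible". Item VII of Intervention limits blinding to two parties: "The patient and the clinician who will assess the end of treatment outcome will be blinded to treatment allocation".

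Under Missing data and non-compliance, "All efficacy analyses will be done intent-to-treat", with as-treated analyses as sensitivity. That section also plans to compare missing-data patterns between arms and to run sensitivity analyses with several imputation approaches, and it expects little missing data.

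**The concern.** Intent-to-treat analysis of a Day 28 score needs that score for everyone randomized. Item III allows a randomized patient to be taken out of the study on two grounds that have no written criterion, non-compliance and data integrity. The investigator is not among those named as blinded. Treatment is one unit of plasma, so once it has been given, withdrawal can in effect end only assessments and follow-up. Non-compliance at that stage gives no treatment reason to stop recording the outcome.

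If the decision to withdraw depends on both arm and clinical course, the missing scores are informative, and comparing the remaining patients is no longer a comparison of randomized groups. The result drives a go/no-go decision, and the plan allows these data to be carried into a phase 3 analysis.

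**Working it through.** **What the sections say together.** Item III gives the investigator the decision. Intervention, item VI, and Randomization put knowledge of the arm with the study team and the Principal Investigator. Definitions ends enrolled status at discontinuation. No section separates stopping study procedures from stopping outcome collection, and none says that Day 28 status will, or will not, be obtained after withdrawal. A blinded assessor protects the scores that are recorded; it does not supply those that are not. The missing-data section gives no rule for a missing Day 28 score in the primary test.

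**The plan's own figure.** The documents give no withdrawal rate and no allowance for loss. The nearest figure is the power of about 82% (219 patients, odds ratio 1.7, one-sided 15% level). The proportional-odds formula for 2:1 allocation is

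power = Φ(√[N × (2/9) × (1 − Σp³)/3] × ln OR − z).

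The Day 28 distribution is not printed. For an assumed 55/10/3/4/3/5/20% over categories 1 to 7, Σp³ = 0.1756, and √(219 × 0.2222 × 0.8244/3) × 0.5306 − 1.0364 = 0.904, so power is 0.817. Five assumed distributions give 0.79 to 0.86 at the 15% level. The stated 82% is consistent with these but cannot be strictly reproduced.

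**Illustration of informative loss.** Inputs:
- 146 versus 73 patients (Statistical Analysis, item 1).
- Thresholds of 15% (power statement) and .015 (go rule). These disagree, which is a separate point to reconcile, so both are shown.
- An assumed Day 28 distribution of 22/30/5/8/5/10/20% in both arms. The 20% deaths match the mortality assumed in Statistical Analysis, item 2; the rest is assumption.
- The number and kind of patients lost, also assumed.

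A tie-corrected one-sided Mann-Whitney test was simulated 40,000 times with no true effect, ignoring country strata. False-go rates:

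| Patients lost | 15% level | .015 level |
|---|---|---|
| None | 14.9% | 1.5% |
| 4 active would-be deaths | 22.7% | 3.1% |
| 4 active and 2 control would-be deaths | 15.5% | 1.8% |
| 4 active patients at random | 14.8% | 1.5% |
| 4 active category 1 patients | 9.8% | 0.8% |
| 4 control would-be deaths | 6.0% | 0.4% |

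With 2, 4 or 6 active would-be deaths lost, the 15% level becomes 18.6%, 22.7% or 27.3%.

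**Check by hand.** Under the null, the expected share of pairs favoring the active arm is 0.5. An active patient in category 7 contributes 0.20/2 = 0.10. Without four of them the share is (146 × 0.5 − 4 × 0.10)/142 = 0.5113. With Σp³ = 0.0474, its standard error is √[216 × 0.9526/(12 × 142 × 73)] = 0.0407. The shift is 0.0113/0.0407 = 0.277, and Φ(0.277 − 1.036) = 22.4%, close to the simulated 22.7%.

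This case is adverse but not an upper bound. Four control category 1 patients contribute 0.22/2 = 0.11 each. The share becomes (73 × 0.5 − 4 × 0.11)/69 = 0.5226, with standard error √[216 × 0.9526/(12 × 146 × 69)] = 0.0413. The shift is 0.548, and Φ(0.548 − 1.036) is about 31%.

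**What harmless loss looks like.** If outcomes are kept after withdrawal, the error rate stays nominal. With 5% lost at random from both arms (three assumed distributions), it is 14.9% to 15.1%, and power is 0.78 to 0.84 against 0.80 to 0.86 with no loss.

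**The case against.** A reader might infer that item III removes withdrawn patients from Day 28 follow-up and so undoes the intent-to-treat analysis. The documents do not support that. Definitions assigns status labels; it does not say what data are collected or who is analyzed. The missing-data section keeps every efficacy analysis intent-to-treat, makes as-treated analysis a sensitivity analysis, compares missingness by arm and plans imputation. The documents are silent on outcome collection after withdrawal; they do not forbid it.

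A reader might also infer that such withdrawals would favor the active arm. Nothing in the documents says which patients would be withdrawn. A death before Day 28 counts as completion, so only a withdrawal made before the death could lose it. Inpatients remain observable, and missed procedures are at least as plausible among discharged patients at the good end of the scale. As the table shows, the error rate can move either way or hardly at all.

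Three further points stand. Not replacing withdrawn patients is consistent with intent-to-treat and is no defect. The patient and the outcome assessor are blinded. A monitoring board reviews conduct quarterly.

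These arguments limit the claim but do not close the gap. Comparing missing-data patterns can reveal a problem after the fact, and unspecified sensitivity imputation does not recover an outcome that a record check could have supplied.

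**Conclusion.** The point holds as a risk that is cheap to remove. Discretionary withdrawal of randomized patients, by a team that knows the arm and with no stated Day 28 follow-up afterwards, can leave the primary outcome missing in an arm-dependent way. That puts the intent-to-treat comparison at risk; it does not void it.

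The size cannot be known from the documents. Four active-arm patients are 4/146 = 2.7% of that arm. If all four were would-be deaths and the control arm lost none, the false-go rate would rise by about half at the 15% level (22.7/14.9 = 1.5) and about double at .015 (3.1/1.5 = 2.1). Proportional or random loss leaves it nearly unchanged, and loss in the opposite direction lowers it. All of this rests on an assumed outcome distribution, assumed withdrawals, and a test without country strata.

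**What to change.** In Subject Withdrawal, item III, state that withdrawal by the investigator ends study procedures only, and that non-compliance or concern about data integrity does not end outcome follow-up. Add that every randomized patient who has not withdrawn consent for follow-up has Day 28 status obtained from records or by telephone (vital status, hospitalization, oxygen support, activity level) and is analyzed as randomized. Report withdrawals by arm and reason. A line under Missing data and non-compliance saying how the primary test treats a score that is still missing would complete the change.

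The cost is a few sentences of protocol text and a record check or telephone call for a few patients. Sample size and the primary test are unchanged.

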1.1.1. Inclusion Criteria for Enrollment

1. Willing and able to provide written informed consent prior to performing study procedures or have a legally authorized representative available to do so.
2. Age ≥ 18 years.
3. Evidence of SARS-CoV-2 infection by PCR test of nasopharyngeal swab or oropharyngeal swab/tracheal aspirate sample within 14 days of randomization.
4. Peripheral capillary oxygen saturation (SpO_2) $\leq 94\%$ on room air or requiring supplemental oxygen, non-invasive or invasive mechanical ventilation at screening.
5. Evidence of infiltrates on chest radiography.
6. Females of childbearing age and males must be willing to practice an effective contraceptive method or remain abstinent during the study period.

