- Most reactions to plasma are relatively minor and the infusion can generally be continued. Infusion site burning and non-allergic systemic effects can generally be managed with slowing of the infusion. Infusion is generally stopped in cases of itching; participant is treated and then infusion cautiously re-started.
- Severe allergic reactions generally require discontinuation of the infusion. These include:

 - Respiratory compromise: dyspnea, wheezing, stridor, hypoxemia A decrease in systolic blood pressure to < 90 mmHg or $>30\%$ decrease from baseline or a diastolic drop of $>30\%$ from baseline.
 - Tachycardia with an increase in resting heart rate to > 130 bpm; or bradycardia.

Concomitant medications will be documented on the CRF:

- Prescription medications
- Over the counter medications
- Herbal treatments/nutritional supplements
- Blood products

Prohibited Medications:

Any approved or investigational drug* with established or potential activity against SARS-CoV-2 given within 24 hours of plasma infusion. *Concurrent use of Remdesivir as treatment for COVID-19 during the course of the study is permitted.

STATISTICAL CONSIDERATIONS AND DATA MANAGEMENT

Design Overview

This randomized blinded phase 2 trial will assess the efficacy and safety of anti-SARS-CoV-2 plasma among adults with severe COVID-19. Eligible participants will be randomized in a 2:1 ratio to receive anti-SARS-CoV-2 plasma or fresh frozen plasma without known anti-SARS-CoV-2 antibodies. We plan to enroll up to 220 participants (US and Brazil). Each participant will be evaluated at baseline and daily during the follow-up period using a seven-category severity scale: 1. Not hospitalized with resumption of normal activities, 2. Not hospitalized, but unable to resume normal activities, 3. Hospitalized, not requiring supplemental oxygen, 4. Hospitalized, requiring supplemental oxygen, 5. Hospitalized, requiring high-flow oxygen therapy or noninvasive mechanical ventilation, 6. Hospitalized, requiring extracorporeal membrane oxygenation (ECMO), invasive mechanical ventilation, or both, and 7. Death.

According to the inclusion/exclusion criteria, all enrolled participants will have a score ranging 3–6 on this scale at baseline. The primary study endpoint is defined as the Day 28 outcome on the scale.

Safety will also be evaluated daily. Secondary endpoints include:

- SARS-CoV-2 PCR positivity from nasopharyngeal swab, collected on baseline (Day 0), Days 7, and 14.

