- Levels of SARS-CoV-2 RNA on Days 0, 7, and 14.
- Duration of need for supplemental oxygen and/or mechanical ventilation
- Duration of hospitalization
- Mortality.

Statistical Analysis

• Efficacy Objective

1. Primary Analysis, go/no-go decision, and power consideration

The primary analysis of the endpoint will be a one-sided nonparametric stratified Mann-Whitney test; stratification is done by country (US, Brazil). A “go decision” in this phase 2 trial will be a one-sided $P < .015$, suggesting evidence of promise of the treatment arm for further investigation in a phase 3 trial. Adaptive seamless phase 2/3: The results in this proof-of-concept study will be used to plan the sample size in a Phase 3 trial, which may include the data in this Phase 2 in the final analysis using adjusted P value as in a seamless phase 2/3 trial. Details of P value adjustment and sample size calculation will be decided before the final analysis of this study data.

The calculation was based on blinded pooled data of the Day 28 outcome and an odds ratio of 1.7 under a proportional odds assumption. With a 2:1 randomization ratio and a total sample size of 219 participants (146 in convalescent plasma vs. 73 control), a onesided Mann Whitney test at 15% level will have about 82% power to detect an odds ratio of 1.7. Since the difference in power between 219 and 220 is minimal, $N=219$ can be used to justify an enrollment total of 220. We note a recent study of antiviral drug yields an odds ratio of 1.15, with 95% CI: 0.67 to 1.96, which covers our assumed odds ratio.

2. Secondary and Ancillary Analyses

All secondary and ancillary efficacy analyses will also be intent-to-treat. With a sample size of 220, assuming 20% mortality up to day 28, we expect a total of 43 events. Longitudinal data collected over multiple days during the study period (e.g., PCR positivity, RNA) will be analyzed using the framework of generalized linear mixed model. Time-to-event variables (e.g., time to death) will be analyzed using Cox proportional hazards model. Continuous variables (e.g. duration of hospitalization) will be analyzed using Mann Whitney test. Treatment effects on these variables will be estimated with 95% confidence intervals.

3. Safety Analyses

Serious adverse events will be summarized by grades and types using proportions and 95% confidence intervals for the two study arms. Relative safety profile of the two arms will be compared using Fisher's exact test.

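### The primary test is valid but leaves the baseline seven-point score unused; stratifying by a pre-randomisation score as well as country would be a cheap improvement

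*Combined protocol and SAP*

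**What the plan says.** Statistical Analysis, item 1, defines the primary test: "The primary analysis of the endpoint will be a one-sided nonparametric stratified Mann-Whitney test; stratification is done by country (US, Brazil". This matches the Randomization section, which uses "random permuted blocks of random block sizes, stratified by country (US and Brazil".

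Design Overview says that "all enrolled participants will have a score ranging 3–6 on this scale at baseline", and that the primary endpoint is the Day 28 outcome on the same scale. The score is scheduled under Study Procedures, Baseline (Randomization). Item 1 there begins "Randomization of eligible subject 2. Vital signs"; the score is item 5: "New medical conditions, concomitant medication 5. Assessment of clinical status (using 7-point ordinal outcome scale". The Screening list, headed "Screening (must be completed before randomization", does not include the score. Inclusion criterion 4 does ask for SpO2 at or below 94% on room air or "requiring supplemental oxygen, non-invasive or invasive mechanical ventilation at screening".

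No efficacy analysis is stated to use the baseline score. The secondary models name no covariates, and the sensitivity analyses cover imputation and as-treated only. The one covariate adjustment in the plan is under Halting Criteria: a conditional interim analysis of need for mechanical ventilation, with age and cardiopulmonary comorbidities named.

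Assignments are "sent to the Principal Investigator/research team for each participant that is deemed eligible", and Intervention item VI says the clinical study team is not blinded. Item VII says the patient and the clinician assessing the end-of-treatment outcome are.

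**The concern.** A baseline value on the endpoint's own scale is a natural candidate for a prognostic covariate. Scores 3 to 6 run from hospitalised without oxygen to invasive ventilation or ECMO, and only 73 patients are controls. Two things could follow from leaving the score out.

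First, precision: if the score predicts Day 28 status, a test that ignores it is less efficient than it could be.

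Second, the one trial that is run may by chance have arms that differ in baseline severity. The go decision rests on a single P value, and these data may be carried into a phase 3 analysis. An adjustment chosen after unblinding would not be credible, so the correction has to be named beforehand or not used.

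**Working it through.** **Inputs from the documents.** 146 versus 73 patients, odds ratio 1.7, one-sided 15% level, about 82% power, 20% mortality assumed by Day 28, baseline scores 3–6.

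**Assumed inputs.** The documents do not give the Day 28 proportions, baseline mix, prognostic strength or country split. The assumptions are:
- Day 28 distribution for scores 1 to 7 of 54/11/3/5/2/5/20%, chosen to reproduce the stated power with 20% deaths
- baseline scores 3/4/5/6 of 8/52/22/18% (mix 1) or 5/80/10/5% (mix 2)
- two thirds of patients in the US
- proportional odds, with 1.7 read as the marginal odds ratio

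**1. The plan's own figure.** By the Whitehead formula, power = Φ(ln OR × √V − z), with V = n1·n0/(3N) × (1 − Σp³).
- n1·n0/(3N) = 146 × 73/(3 × 219) = 16.22
- 1 − Σp³ = 0.833, so V = 13.51 and √V = 3.676
- ln 1.7 × 3.676 − 1.036 = 1.950 − 1.036 = 0.914, and Φ(0.914) = 82.0%

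This shows that 82% at the 15% level is attainable. It does not recover the sponsor's unpublished proportions.

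**2. Validity.** In simulation with no treatment effect, overall false go was 14.9–15.1% with country strata and with added baseline strata.

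**3. Power.** Van Elteren tests, 60,000 simulated trials per setting, 15% level. Each entry is country only → country × two baseline levels (3–4, 5–6).

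| Odds ratio per baseline category | Mix 1 | Mix 2 |
|---|---|---|
| 1 | 82.6 → 82.2% | 82.5 → 82.1% |
| 1.5 | 82.5 → 82.9% | 82.3 → 82.4% |
| 2 | 82.3 → 84.3% | 82.5 → 82.9% |
| 3 | 82.2 → 87.3% | 82.6 → 84.2% |

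Three levels (3–4, 5, 6) give −0.6, +0.3, +2.2 and +5.5 points in mix 1, and −0.7, −0.1, +0.3 and +1.8 in mix 2. Two levels therefore keep nearly all of the gain.

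**4. How often a severity imbalance arises.** The arm difference in the share with scores 5–6 has SD √[q(1−q)(1/146 + 1/73)].
- Mix 1, q = 0.40: SD 7.0 points, so 10 points or more in one direction is 1.42 SD, or about 8% of trials.
- Mix 2, q = 0.15: SD 5.1 points, 1.95 SD, or about 3%.

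**5. False go within those trials, no true effect, 15% level, country-only test.**

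| Odds ratio per category | Favouring plasma, mix 1 | Favouring plasma, mix 2 | Against plasma, mix 1 | Against plasma, mix 2 |
|---|---|---|---|---|
| 1.5 | 23% | 21% | 9% | 9% |
| 2 | 29% | 27% | 6% | 7% |
| 2.5 | 35% | 31% | 4% | 5% |
| 3 | 39% | 35% | 3% | 4% |

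With baseline strata every entry is about 15–16%.

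**6. Sparse cells.** With two levels, the median smallest control cell is 9 (mix 1) or 3 (mix 2), and 4 or 2 if 85% of patients are in the US. Overall false go with two-level strata was still 14.9–15.3%, so sparseness does not threaten validity. A minimum-count rule would be a poor safeguard: a 15-patient minimum would still fail after merging 5 with 6 in 71–100% of trials in three of the four scenarios.

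**7. Timing of the score.** Study Procedures lists the assessment after randomisation, but does not say that the items are in time order or who scores baseline. Criterion 4 supplies oxygen or ventilation status at screening but does not name high-flow oxygen. Separating 4 from 5 therefore needs the pre-randomisation oxygen-device record.

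**The case against.** The strongest reply is that nothing is wrong. The test stratifies by exactly the randomisation factor, which is standard practice. Overall false go is unchanged, the power claim stands, and the gain may be nil. All of this is correct, and it is why the point is an improvement only.

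The sizes do rest on assumptions. At an odds ratio of 2 or less per category, the power change is about 2 points at most. The 23–39% figures apply only to trials selected for an imbalance favouring plasma; the mirror cases fall to 3–9%. A reader might infer that the planned test inflates type I error or that the trial is underpowered. Neither follows.

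The imbalance argument applies to any unadjusted prognostic factor, including age. That is also true. The score is singled out because it is on the endpoint's scale and is already scheduled for every participant.

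A reader might also infer that the baseline score is taken after allocation and coloured by it. The documents do not establish this, because list position is not a stated time order and the scorer is not named. What stands is narrower: the plan does not guarantee a pre-randomisation score, and the clinical study team is unblinded. Adjustment is therefore safe only if the timing is stated. It is also fair that the Screening list names no oxygen-device item, so feasibility has to be checked.

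**Conclusion.** The point holds as a limited gap in precision and robustness. Under the assumptions shown, at the 15% level, baseline strata cost up to about 1 point of power if the score carries no information. They gain 0 to 2 points at an odds ratio of 2 per category and about 2 to 6 at 3, depending on baseline mix and number of levels. They also hold false go near 15% in the roughly 8% (mix 1) or 3% (mix 2) of trials where a chance imbalance would otherwise raise it to 23–39% or 21–35%.

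Confidence is medium, because the baseline mix and prognostic strength are not in the documents. The go rule is written as P < .015 while power is given at 15%. That conflict is a separate matter, but the same pattern appears at .015: with an imbalance favouring plasma, false go is 3.0–6.8% (mix 1) or 2.7–6.1% (mix 2), against about 1.5% with three-level baseline strata.

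**What to change.** Before unblinding, have staff blinded to allocation document one primary test, for example: *a one-sided van Elteren test of the Day 28 score, stratified by country and by baseline score (3–4 versus 5–6), where the baseline score reflects clinical status recorded before the time of randomisation.*

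- Set no minimum cell size. Strata that contain only one arm contribute nothing.
- Name the source of the score: screening oxygen and ventilation data, with the oxygen-device record to separate 4 from 5.
- Keep the country-only test as a sensitivity analysis.
- If a pre-randomisation score cannot be established for nearly all patients, keep the country-only test as primary and pre-specify the baseline-stratified test as supportive.

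The cost is up to about 1 point of power if the score is uninformative, a little analysis work, and a check of when each score was recorded. Because pooled Day 28 data have already been used for the sample size and the clinical team is unblinded, the record should show who made the decision and that they were blinded.
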